To evaluate the impact of the game in this Phase II study, we will conduct a randomized controlled trial (RCT) enrolling 200 clients randomized to *OTG* or a control condition of *RVs* in a 1:1 ratio. We will recruit these participants from OnTrackNY's Early Intervention for Psychosis (EIP) clinical centers after screening for eligibility. After consent and initial interview (baseline), participants will be randomly assigned to either *OTG* or *RV*. Following an intent-to-treat framework, we will then assess each client participant at 2 additional time points regardless of participation in their assigned condition: post-intervention at 2 months and follow-up at 5 months after baseline. Ten clinicians working with these clients will also be recruited for semi-structured key informant qualitative interviews. Our rationale for selecting a randomized controlled design stems from our Phase I findings, which suggest that the game may be effective in addressing young people's hopefulness, stigma, and understanding around first episode psychosis. An RCT design will allow us to examine how specific aspects

of the game impact outcomes in these areas, as compared to more static, passive online resource.

Subjects, Sampling, and Recruitment

Subjects

OnTrackNY is New York State's coordinated specialty care (CSC) program. Funded by state dollars, a SAMHSA Healthy Transitions Grant, and Mental Health Block Grant funds, the state currently supports 13 teams throughout the state. Eight additional programs are expected to come on line within the next 6 months. The program serves young adults ages 16 to 30.

At the time of funding, we expect 14 CSC sites to be located in downstate New York. Although sites will have different numbers of clients (20–40), approximately 450 clients will be participating in the program at that time. Based on the 2-year program, approximately 225 new clients will start the program during the year of recruitment. Based on our previous experience, we believe we will be able to recruit 33% of the eligible clients. If for some reason, we fall short of our recruitment goals, we will use the other OnTrackNY sites until we meet our goal. We anticipate no challenges in recruiting clinicians (n=10).

Sampling

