Client Inclusion Criteria: Client study participants will be individuals currently enrolled in OnTrackNY who wish to enroll and who meet these inclusion criteria: (1) between the age of 16 and 30; (2) receiving services at one of the host sites; (3) able to give fully-informed consent; (4) willing and available to take part in the intervention conditions, 3 in-person quantitative assessments, and possibly a semi-structured qualitative interview; (5) engaged in the EIP program for less than a year; (6) access to the internet with a personal computer or tablet (if this is a barrier, sites can provide access); (7) access to email; and (8) are English speaking. **Exclusion criteria:** Not meeting inclusion criteria. RAs will screen each interested individual and schedule a consent appointment if interested and eligible.

Clinician Inclusion Criteria: Clinician criteria include mental health professionals who (1) are providing care in a host site and working with a client participating in the study, (2) are willing to complete study requirements and provide signed informed consent, and (3) are English speaking.

Review of participant enrollment and compliance with inclusion/exclusion criteria will occur monthly during recruitment to ensure that a sufficient number of participants are being enrolled and that they meet eligibility criteria and the targeted race and ethnic diversity reflected in the enrollment tables of the proposal (see Targeted Enrollment tables in proposal).

Recruitment

We will recruit client participants via flyers and announcements at the sites, clinician referrals, and review of clinic rosters (after obtaining a partial HIPAA waiver). After explaining the study, RAs will screen interested clients and schedule a consent appointment if indicated. All RAs are trained in informed consent procedures and will explain participation risks and benefits, confidentiality risks and protections, the voluntary nature of participation, that participating or not will not affect one's services, and that the participant may withdraw at any time with no penalties. RAs are trained and supervised regarding informed consent with people with psychosis who may have cognitive, attention, and processing difficulties. RAs will administer a brief questionnaire to verify that the person is competent to provide consent and demonstrates comprehension of the consent document. If the client does not answer all questions correctly,

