Following informed consent, the RA will open the envelope indicating to which intervention the participating client was randomized. For people in the *OTG* condition, the RA will review an outline of the game, provide directions on how the game works, and reiterate the expectation that the participant will finish the game in the following 2 months, if not sooner. We expect that spending 1 hour a week playing the game will be sufficient to complete all levels of the game. For participating clients in the *RV* condition, they will be reminded that they are expected to view the recovery videos and download the information materials from the website. We anticipate that the materials could be viewed in approximately 4 hours. The RA will remind the participant that they will receive an email with a link to either the game or the website, depending on their study condition. All participants will be provided with an email address and telephone number. If a participating client does not open the email with the link for 2 weeks, another email will be sent.

Intervention Description (OTG)

The intervention condition will consist of 2 components: (1) provision of the game to the participating clients via an email link, and (2) brief interactions with their mental health provider with respect to reactions they may have when playing the game. Components of the game are described in the *Innovation* section of the proposal. The participant will be reminded via email once a week to play the game/visit the website for a period of 2 months. After that time,

reminders to play the game/visit website will no longer be sent, but the participant may continue to play if they wish.

Control Condition (RV)

The control condition will consist of access to a website that will contain the recovery videos and the static information that is contained in the game. In the control condition, mental health providers will also ask about possible reactions to viewing the recovery videos and information on the website. At the end of the study (after the follow-up assessment), the *RV* participants will be provided access to the game. The table below shows how the conditions align.

Component	OnTrack>The Game (OTG)	Recovery Videos Website (RV)
1. Testimonials of Hope and Recovery	Movie theater zone with 20 brief (3–5 minute) video interviews with young adults who have experienced psychosis.	Online library of the 20 video interviews from OTG

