Client interviews: A subset of 10 clients from each study condition (n=20) will be asked to participate in semi-structured interviews after using *OTG* or *RV*. Questions will explore their experiences in using the product (navigation and access, preferences, facilitators and barriers to use); attitudes toward treatment and working with their clinician; and their feelings of self-efficacy, recovery, hope for the future, and stigma. Clients will receive \$25 for participating in these interviews.

Clinician interviews: Ten clinicians, working with clients from both study conditions, will also be asked to participate in semi-structured interviews to explore their experiences in working with clients from each condition and changes in attitudes they may have observed, barriers and facilitators to use of each product, and feedback on the product components. Clinicians will receive \$50 for participating in these interviews.

We feel that the number of interviews described will be sufficient to reach data saturation, but we will add interviews if needed.

Quantitative: Baseline, post, and follow-up surveys will be completed with each study participant via in-person interviews using direct data entry into a secure online database built with Qualtrics software. Baseline assessment will occur at the time informed consent is obtained if possible, and at this time we will ask participants for demographic data including age, gender, race and ethnicity, education level, relationship/marital status, work, and school participation. Data on treatment engagement will be extracted from clinic charts.

The following table presents domains, measures, and time-points for administering them.

Quantitative Measures and Frequency of Assessments by Specific Aim				
Domain	Measure	Administered at study time-point		
		BL	Post	Follow-up
Aims 2 and 3				
Stigma Concerns	Rüsch Stigma Stress	x	x	x
	Questionnaire on Anticipated Discrimination			
Empowerment	Recovery Attitude Questionnaire (RAQ)	x	x	x
	Roger's Empowerment Scale Total			
	Herth Hope Index (HHI)			
Treatment Engagement	Singh O'Brien Level of Engagement Scale (SOLES)	x	x	x

	Number of unduplicated visits during the follow-up period is above engagement threshold			x
Description of Sample and Potential Moderators and Mediators				
Participant Demographics	Demographic Form/Chart Review	x		
Experience with Game Functionality and Design	EGameFlow		x	x
Use of Game/Website	Springroll Learning Module/Google Analytics		x	x

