Data Analysis

All data will first be screened for errors via frequency and contingency tables and univariate and bivariate plots. These will also allow us to check for missing data and that variable distributions are compatible with the statistical models we will use.

Triangulation increases confidence in the validity of a finding if it converges across disparate sources of information. Qualitative data will be triangulated by sources (comparing client and clinician interview data). Further, the research team will also actively work to integrate quantitative and qualitative datasets, comparing results during and after analysis, to allow for ongoing interpretation.

We will use a mixed-effects, 2-level model (SAS Proc Mixed, GLIMIX) to test primary hypotheses with a random class effect to account for intra-team correlation (ICC). The longitudinal assessments (baseline (t=1), post-treatment (t=2), and 6-month follow-up (t=3)) will be nested within participants and participants nested within teams. Adjustment for baseline response will reduce residual variation at t=2 and t=3 resulting in greater power. Correlation in the response at t=2 and t=3 (conditional on response at t=1) will be modeled by allowing the corresponding error terms to be correlated rather than using a random individual effect. That is, we will use a hybrid model with both a random class effect and correlated error terms (conditional on baseline value and the class effect).

Quantitative Analysis

Aim 2: A Generalized Linear Mixed Model will be used with the outcome measures listed above as the dependent variables and treatment group (*OTG* vs. *RV*) as the independent variable of interest. Baseline outcome measures and any covariates determined from preliminary analyses will also be included in the model. Post hoc analyses will include assessment of treatment group differences in the outcome measures at post-intervention and 3-month follow-up. Engagement will be binary variable; therefore a log link will be employed. The test of hypothesis 1 and 2 will operationally be the test of whether the coefficient of the *OTG/RV* condition term is significantly greater than zero (2-sided test) for each contrast.

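### The recruiting role opens the allocation envelope with no described concealment, and the protocol's wording allows the arm to be revealed before baseline is measured

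*Combined protocol and SAP*

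**What the plan says.** - **Who recruits.** Under Recruitment, "RAs will screen interested clients and schedule a consent appointment if indicated". The same role decides whether a client passes the consent check: "RAs will administer a brief questionnaire to verify that the person is competent to provide consent". A client who fails is given clarification and one more attempt, and is not enrolled after a second failure.
- **Who reveals the arm.** Under Study Conditions, once consent is given, "the RA will open the envelope indicating to which intervention the participating client was randomized". The RA then explains the assigned condition, and clinicians are asked to enquire about it, so neither is blind.
- **The allocation rule.** Research Design describes "enrolling 200 clients randomized to *OTG* or a control condition of *RVs* in a 1:1 ratio". No sequence generation, envelope specification, blocking or stratification is described.
- **The order of events.** Research Design places random assignment after both consent and the baseline interview. Study Conditions places the envelope after consent and does not mention baseline. Data Collection (Quantitative) has baseline done at the consent visit only where feasible.
- **What the analysis uses.** Data Analysis adjusts for the baseline response and includes a random effect for team.
- **What is already in place.** Assessments use "direct data entry into a secure online database built with Qualtrics software".

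**The concern.** Two things are at stake.

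The first is concealment. The role with some influence over whether and when a client enters is also the role that reveals the arm and sees the arms already assigned. If the next arm could be read or guessed, entry could differ by arm, and the outcomes are mainly self-reported. The protocol states no safeguard that would let a reader rule this out.

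The second is the order of baseline and allocation. The baseline scores are covariates in the outcome model. If some clients learn their arm before rating hope, empowerment and stigma, those ratings can respond to the arm and are no longer true baseline values. A client could also withdraw after learning the arm and before giving any baseline data.

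**Working it through.** **1. The order, with the three sections side by side**

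| Section | Order given |
|---|---|
| Research Design | consent, baseline, random assignment |
| Study Conditions | consent, envelope opened |
| Data Collection (Quantitative) | baseline at the consent visit where feasible, otherwise later |

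If baseline is deferred and the RA follows Study Conditions, the order is consent, envelope, baseline. This contradicts Research Design. In a model with baseline slope b, the adjusted arm effect is (outcome difference) minus b × (baseline difference). If knowing the arm shifts the baseline difference by d, the estimate moves by −b·d. The documents give neither d nor the proportion of deferred baselines, so no number can be attached.

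**2. Steering, as a hypothetical only**

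The plan's 200 cannot be reproduced, because no alpha, power, effect size or SD is given. For scale, assume two-sided alpha 0.05, 80% power, no attrition and no covariate adjustment. The detectable difference is then 2.80 × √(4/200) = 0.396 SD.

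- Suppose 10 of 100 game clients are 0.5 SD better and 10 of 100 video clients 0.5 SD worse because of steering. The bias is 0.10 × 0.5 + 0.10 × 0.5 = 0.10 SD, about a quarter of 0.40 SD. These inputs are invented, the case requires foreknowledge of the arm, and it ignores the planned baseline adjustment.
- More generally, bias = s × (2q − 1). Here q is the chance of guessing the next arm correctly, and s is the prognostic gap between clients entered under the two guesses.
 - Contents unknown and unguessable: q = 0.5, bias 0.
 - Fixed blocks of 4 that can be tracked: q = (1/2 + 2/3 + 2/3 + 1)/4 = 0.708, bias 0.417s. This is 0.08 SD for s = 0.2 and 0.21 SD for s = 0.5.
 - Envelopes readable in advance: q = 1, bias 0.2 to 0.5 SD for the same s.

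**3. Balance within teams, if allocation is simple**

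The plan says "we expect 14 CSC sites to be located in downstate New York", so 200/14 is about 14 per team. Sites will differ in size, so equal teams are an assumption.

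- A split of 10:4 or worse in a team of 14: 2 × P(X ≤ 4) = 2 × 1471/16384 = 0.180.
- At least one such team of 14: 1 − (1 − 0.180)^14 = 0.94.
- Variance of the arm effect (generalised least squares with a random team effect), simple allocation relative to blocks of 4 within team: 1.018, 1.031, 1.044 and 1.055 for ICC 0.02, 0.05, 0.10 and 0.20. If the overall split is held at 1:1, the ratios at the two ends are 1.013 and about 1.05.

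The 94% describes chance imbalance, which does not bias the comparison. The cost is about 2-5% of variance, or roughly 4-10 clients.

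**4. What blocking within team does to concealment**

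Take a team of 14 and someone who sees earlier arms and guesses the under-represented one. With blocks of 4, accuracy is (12 × 0.708 + 2 × 0.583)/14 = 0.69. Here 0.583 is the mean of 1/2 and 2/3 for the two places in the incomplete last block. Simulation with small varying blocks (4/6 or 2/4/6) also gives about 68-69%. Simple allocation gives 50%.

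**The case against.** The strongest reply is that envelopes opened after consent can conceal allocation perfectly well, and nothing in the text says that they are unsealed, readable or held by the RA beforehand. The wording is compatible with an envelope prepared in advance by someone else. Eligibility is largely factual, the comprehension check has a fixed pass rule, and enrolment and eligibility are reviewed monthly. The documents show one role, not necessarily one individual. The protocol also refers to a fuller proposal that is not available here. All of this stands.

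A reader might infer three stronger claims, and the documents support none of them.

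- **That allocation is unstratified.** The protocol is silent on this; it does not say so.
- **That entry will be steered.** This needs foreknowledge of the next arm, which the text does not show.
- **That any such bias is beyond repair.** The planned baseline adjustment would remove the part captured by baseline scores, provided baseline truly precedes allocation. Only differences not captured there, such as motivation, would remain.

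The reply does not answer two points. The protocol has the recruiting role open the envelope without stating a safeguard, and its three descriptions of the order do not agree.

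**Conclusion.** The point holds as a weakness in the allocation procedure and an inconsistency in its timing; it is not evidence of bias. On the current wording the arm can be revealed before the covariates are measured, and concealment cannot be verified.

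The size of any bias is unknown. It is zero if the next arm cannot be known or guessed. The 0.08-0.21 SD and 0.10 SD figures are conditional on foreknowledge and on assumed prognostic gaps, and they are before baseline adjustment.

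Lack of team stratification, if that is the case, is a minor matter of precision (about 2-5% of variance, assuming simple allocation, 14 teams of 14 and ICC 0.02-0.20). Stratified blocks would themselves make the next arm partly guessable. The change is worth making because it is cheap and protects the whole comparison, but a sound procedure may already exist unwritten.

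**What to change.** 1. Have someone outside recruitment generate the list, and hold it where RAs cannot see it.
2. Release the arm only after consent and baseline have been submitted for that ID. Use the study database if it can lock and hide the list, which the protocol does not establish. Otherwise use sealed, opaque, sequentially numbered envelopes with each opening logged.
3. Align Research Design, Study Conditions and Data Collection on one order: consent, baseline, release of the arm.
4. State whether allocation is blocked or stratified. Stratifying by team is optional. If it is used, make the blocks large or varied and do not disclose their sizes to recruiting staff.

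The cost is a few protocol sentences and the set-up of one form, or the preparation of the envelopes. Database release needs a connection at the visit, which direct data entry into an online database already requires. If these safeguards exist, writing them down is enough for steps 1, 2 and 4.

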develop and test a prototype version of *OnTrack>An Online Role-Playing Game* (*OnTrack>The Game* or *OTG*), an online role-playing game designed for youth and young adults experiencing FEP. The Phase I SBIR (NIMH #1R43 MH105013-01) brought together C4's experience developing innovative learning technologies with the subject matter expertise of [name] and her team. Phase I showed positive changes in quantitative measures of hope and recovery, as well as an enthusiastic response to the prototype as evidenced by qualitative interviews (see *Significance* section in full proposal). These findings suggest the need for and feasibility of conducting a Phase II study.

The proposed mixed-methods Phase II study will use standardized measures and semi-structured qualitative interviews to achieve the following aims:

1. **Product aim:** To refine, expand, and finalize *OnTrack>The Game*. Building on the Phase I prototype, we will improve functionality, expand the play spaces and levels, add interaction with non-player characters, include more resources on FEP, and expand the library of videos on hope and recovery.
2. **Primary research aim:** To evaluate the effectiveness of a role-playing game (*OTG*) in increasing empowerment, decreasing stigma concerns, and improving treatment engagement.

Hypothesis 1: Compared to control condition (Recovery Videos, or *RV*), participants in *OTG* will report significantly increased empowerment at 2 months post-intervention compared to baseline.

Hypothesis 2: Compared to the control condition (*RV*), participants randomized to the *OTG* condition will report significantly increased empowerment, (Herth Hope Index, Recovery Attitude Questionnaire, Roger's Empowerment Scale), decreased stigma concerns (Questionnaire on Anticipated Stigma, Rüschi Stigma Stress), and greater treatment engagement (Signh O'Brien Level of Engagement Scale, engagement with CSC program) at the 5-month follow-up compared to baseline.

3. **Secondary research aim:** To determine if changes in empowerment and stigma concerns mediate the effect of *OnTrack>The Game* on treatment engagement.

Hypothesis 3: Increases in hope, attitudes toward treatment, and self-efficacy and decreases in stigma concerns at post-treatment will partially mediate the improvement in treatment engagement at follow-up.

METHODS

Research Design

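### The chart-visit engagement outcome has no baseline value, although Hypothesis 2 and the Aim 2 model both call for one; prior attendance and time in program should be pre-specified as covariates.

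*Combined protocol and SAP*

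**What the plan says.** - **Hypothesis 2 (Primary research aim)** names two treatment-engagement measures, the SOLES scale and program engagement. The comparison it states is "engagement with CSC program) at the 5-month follow-up compared to baseline".
- **Measures table (Data Collection, Quantitative)** marks SOLES at baseline, post and follow-up. The other engagement row reads "Number of unduplicated visits during the follow-up period is above engagement threshold" and is marked at follow-up only.
- **Source (Data Collection, Quantitative):** "Data on treatment engagement will be extracted from clinic charts". No period before baseline is mentioned.
- **Data Analysis** describes a model conditional on the t=1 response and gives the reason: "Adjustment for baseline response will reduce residual variation at t=2 and t=3 resulting in greater power".
- **Quantitative Analysis, Aim 2** applies one model to all the listed outcomes: "Baseline outcome measures and any covariates determined from preliminary analyses will also be included in the model". Visits are not excepted. The section adds: "Engagement will be binary variable; therefore a log link will be employed".
- **Client Inclusion Criteria** admit clients who have been "engaged in the EIP program for less than a year". The Subjects section describes a 2-year program.

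**The concern.** For the visit measure, the hypothesis, the schedule and the model do not fit together. Hypothesis 2 and the Aim 2 model need a baseline value, and the schedule produces none. The single mark is unlikely to be a damaged table, because the row itself describes a count over the follow-up period.

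Treatment engagement belongs to the primary research aim, and treatment participation is the Aim 3 outcome. The analyst would have to decide, perhaps after seeing data, what replaces the missing baseline term. Clients will also be at different stages of care when they enter. Differences in prior attendance and program stage then stay in the unexplained variation, and the gain in power that the plan expects from baseline adjustment does not reach this outcome.

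**Working it through.** **1. Schedule against model.**

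| | SOLES | Visits above threshold |
|---|---|---|
| Baseline (t=1) | yes | no |
| Post (t=2) | yes | no |
| Follow-up (t=3) | yes | yes |
| Baseline term can be fitted | yes | no |
| Correlated t=2 and t=3 errors apply | yes | no |

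For visits, the longitudinal model reduces to one time point with a team effect and a condition term. No section defines a pre-baseline visit count, a look-back window, a time-in-program covariate or a separate model for visits.

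**2. What can still be tested.** Aim 2 makes the operational test the two-sided test of the OTG/RV coefficient. That coefficient can be estimated from follow-up data alone. The plan gives 200 clients at 1:1 and 20% attrition at 5 months, so 200/2 × 0.8 = 80 per arm if attrition also affects chart data, and 100 if it does not. The plan has no power figure to reproduce. For illustration, I assume two-sided alpha 0.05, no clustering and 80 per arm:

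| Above threshold, RV vs OTG (assumed) | Power, follow-up only |
|---|---|
| 50% vs 65% | 0.48 |
| 60% vs 75% | 0.53 |
| 70% vs 85% | 0.62 |

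**3. What adjustment could add.** All inputs are assumptions: log visit-rate SD 0.5 between clients, pre/post correlation 0.6, time in program uniform over 0 to 12 months, look-back of up to 3 months, visit rate changing by 0 to −0.08 per month on the log scale, no clustering, and logistic fits to the thresholded outcome. Each simulation compared the condition test with and without prior visit rate and time in program.

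- With about 58% vs 73% above threshold, power rose from 0.56–0.63 to 0.67–0.69 at 100 per arm, and from 0.47–0.56 to 0.54–0.59 at 80 per arm. The gain was about 3 to 12 points, and type I error stayed near 0.05.
- With about one visit a week, a 13-week window, a log-rate effect of 0.22 and thresholds of 6, 9 or 13 visits, the gain was about 0 to 8 points. At the low threshold, with about 90% engaged, it was 0 to 5.
- A further simulation of a thresholded outcome gave about 0 to 10 points.

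About 0 to 10 points is a fair summary, although single settings went slightly higher.

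**4. Spread of time in program.** If it is uniform over 0 to 12 months, the SD is 12/√12 = 3.46 months. With 100 per arm, the standard error of the arm difference is 3.46 × √(2/100) = 0.49, so the 95% chance range is ±1.96 × 0.49 = ±0.96 months. The share with under 3 months of history is 3/12 = 25%.

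**The case against.** The strongest reply is that the randomised contrast is intact. A reader might infer that Hypothesis 2 cannot be tested at all for visits. The documents do not support that, because the operational test is the condition coefficient, which needs no baseline. A reader might also infer that unequal time in program biases the result. It does not: randomisation makes any imbalance a chance matter that the test's error rate already allows for. Both replies stand, and they confine the point to wording, a missing model term and precision.

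A third tempting step is to size the loss by the share of variance explained on log visits. That is arithmetic for a continuous outcome, whereas the plan makes engagement binary, and dichotomising leaves a smaller gain.

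The plan could also be said to leave a route open, through covariates chosen in preliminary analyses and a chart review at baseline listed with demographics. This stands only in part. Time in program could enter that way, but it is not pre-specified. Prior attendance could not, because nobody plans to extract it.

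Finally, the uniform spread is an assumption. The criteria set only an upper limit, and recruitment is sized partly on about 225 new starters in the year. If clients enter mostly early, chance imbalance shrinks, but so does the available look-back.

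**Conclusion.** The mismatch is real and no other section repairs it. It affects only the visit component of treatment engagement; SOLES has its baseline. As written, the comparison with baseline and the baseline term cannot be carried out for visits, while the between-arm comparison at follow-up can.

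The loss of precision is modest: about 0 to 10 points of power under the assumptions above, and least when nearly all clients exceed the threshold. That range rests wholly on assumed inputs, since the documents give no visit rate, threshold value, correlation or ICC. The simulations also used a logit rather than the stated log link. The change is worth making because it is cheap and gives this outcome the adjustment the plan already relies on, not because the trial would otherwise fail.

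**What to change.** 1. From the charts, extract visits before baseline, for example over up to 3 months, expressed as a smoothed rate over the weeks actually available. Also extract the OnTrackNY start date; time in program must already be known to apply the entry criterion.
2. Pre-specify prior visit rate and time in program as covariates in the visit model, for Aim 2 and for Aim 3 where visits are the outcome. State that this model has a single time point.
3. For this measure, word Hypothesis 2 as a between-arm difference at follow-up, adjusted for baseline attendance.
4. Say how clients with little or no look-back are handled, for example with an indicator.

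The cost is one more window in an extraction already planned, plus revised wording; there is no extra assessment for participants. The sponsor should confirm that consent covers the earlier chart period.

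There are two limits. About 25% of clients would have under 3 months of history if time in program is uniform, so their prior rate is noisy or missing, and the time-in-program covariate handles this only partly. If about 90% exceed the threshold, 160 × 0.10 = 16 clients at 80 per arm fall below it, which leaves little room for covariates.

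If the look-back is not adopted, the minimum is to reconcile the three sections: state that visits have no baseline term and drop the comparison with baseline for this measure.
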